4.2 Project Timeline

This study will require approval by the Office of Human Research Protections, the Penn IRB, and the City of Philadelphia IRB, which is used by the Philadelphia Prison System. We will also register this study on clinical trials.gov. We will train research and clinical staff in study procedures, and write the study procedures manual before implementation of any procedures. These activities will be completed by month 3. Randomization and treatment will occur in months 4-33, with data cleaning, analyses, and final reports completed by month 36. This schedule projects an average enrollment of 8.3 subjects randomized/month. This rate is feasible based on the number of opioid addicted individuals that enter the PPS every year; the level of interest in XR-NTX that we identified in our interactions with former or current opioid addicted prisoners (details in other parts of the proposal); the broad enrollment criteria that will not exclude many potential candidates; the staffing requested to implement the study; NET Steps capacity to treat participants; research experience by NET Steps and its leaders, who have met recruitment and follow-up targets in other studies; and support from administrators and staff in the PPS. We have found that that recruitment for clinical trials can be slower or faster than expected at various times thus it is difficult to know exactly what proportions of the final sample will have been recruited at specific points. Our best estimate is that 25% will be recruited by the end of month 9, 50% by the end of month 15, 75% by the end of month 21, recruitment finished by the end of month 27, and treatment finished by the end of month 33.

Interim progress and engagement reports will be submitted every 6 months and include summaries of ways that patients and stakeholders were involved in the development of study materials and implementation of the study according to PCORI requirements. We do not plan to do interim analyses unless requested by PCORI or an

IRB. Final analyses will be completed by the end of month 35 and a final report will be submitted at the end of the contract period. Copies of submitted and published manuscripts will be provided to PCORI staff and de-identified data along with a codebook and analytic data sets made publically available on the clinical trials NIH web site within 9 months of acceptance of the primary outcome paper.

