NET@PPS is part of NET Steps, both part of North East Treatment Centers (NET), a non-profit substance abuse facility that operates 10 programs. NET Steps has an IOP with step down programs for patients in its methadone maintenance and non-agonist programs. NET@PPS staff interacts with thousands of opioid addicted inmates in the PPS each year but only 150-200 are on methadone at the time of incarceration and eligible to receive it from NET@PPS. NET@PPS staff consists of a physician ([name]), who directed substance abuse medication studies at the Philadelphia VA in the Penn/VA Addiction and Treatment Research Center; nurses; a clinical coordinator ([name]); counselors with a maximum of 35 patients as per PA regulations; and support staff. The NET@PPS consists of 5 main facilities and 7 smaller Alternative and Special Detention facilities. Each is under the direction of a warden and all are located on 100 acres in Northeast Philadelphia. The PPS operates on the concept of unit management to reduce inmate movement by delivering services where inmates reside. Most daily functions including dining, outdoor exercise, medication, and sick call are provided on the units. The Inmate Services Division provides counseling, job placement, addiction prevention education, individual, family, and group therapy, AIDS awareness programs, interdenominational religious services, and self-help programs including AA and NA. PPS has a community reintegration program, 14 industrial training programs, and 8 vocational training programs. Prison Health Services provides primary care, including detoxification, HIV, dental, and mental health services. As described above, NET@PPS operates a methadone program for inmates that are on an approved methadone program at the time of incarceration, and has access to all PPS units. The approximately 90% of opioid dependent Inmates that are not on methadone, including those on buprenorphine, are detoxified and referred to treatment at re-entry. The PPS has an approved census of 6800 but typically houses over 8000 due to strict sentencing laws and has been sued in Federal Court for overcrowding. Approximately a third of inmates have been sentenced; others are awaiting sentencing or in for probation violations such as positive drug tests, failure to pay fines or enroll in drug treatment, missing appointments with probation or parole officers, or new crimes. Turnover is rapid, and about 50% are released within two weeks. A total of 240,729 individuals were admitted and released between 1996 and 2003 but this figure represented only 106,849 different persons. About half of these 106,849 were incarcerated and released an average of 3.5 times, accounting for 187,501 incarcerations and releases, or

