Candidates who complete all inclusion procedures will be randomized into two groups; group A who will be scheduled to return to the research office prior to re-entry for a drug test, a breathalyzer test, another pregnancy test (females), and naloxone challenge, and group B who will be scheduled to for a drug test and naloxone challenge after release within 7 days at the NET treatment clinic. Those with a opioid positive drug test will be asked to return in 3 days for a repeat test; failure to have an opioid negative test on the second occasion will count as a relapse. Patients who fall into this category will be referred for other treatment or can be restarted on study medication if they are detoxed and elect to continue. These patients will continued to be followed for their weekly and monthly assessments. Those in group A or B with an opioid negative drug test and who pass the naloxone challenge will receive their first dose of XR-NTX with continuing XR-NTX for 3 months thereafter at NET Steps.. A benefits manager will schedule an appointment with the participant after they have met the inclusion criteria, have been randomized, and have a valid release date. Those who change their mind about XR-NTX will be eligible for methadone, buprenorphine-naloxone, intensive outpatient treatment without medication, or referral to another program if they so choose. If a subject in Group A, who received an injection before release from PPS is held over in PPS pass the expected release date by 30 days but not greater than 6 months, the subject will not be given a second injection inside the prison. The subject will be considered in the study but not injected until the new established release date for his next injection. The injection visit dates will be reset to begin as his first injection, with the next injection post release.

If a subject in Group A, who received an injection before release from PPS is held over in PPS more than the expected release date but less than or equal to 30 days from his first injection, the subject’s next injection will be considered his 2nd injection and his visit schedule will not change.

Table 1: Study Interventions and Assessments Flow Chart

	Months 1-3	Month 6
--	-------------------	----------------

XR-NTX Before Reentry (N=100)	XR-NTX + Therapy + Follow Up	Therapy + Follow Up
XR-NTX After Reentry (N = 100)	XR-NTX + Therapy + Follow Up	Therapy + Follow Up

5.6 Randomization Procedures:

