There are relatively few data to estimate power for this study since so little work has been done in this area. We know that most relapses from various substance dependencies occur in the first 3-6 months ([name] & Cacciola, 1994). For opioid addiction it typically occurs in the first days or weeks (Binswanger et al, 2007) and for opioid addicted prisoners, often on the way home from jail, according to reports from the two Recovery Specialists and

more than half of the focus group participants. We also know that XR-NTX will prevent relapse for a month and that more than twice as many prisoners that did not receive it before reentry relapsed by the second month after reentry as compared with those that received it before reentry (Lee et al, 2013). Regarding the issue of how long patients will continue on XR-NTX, 79% of the XR-NTX patients in the O'Brien et al study received their first 3 injections and 73% received their first 4. In the Krupitsky et al study (2011) 78% received their first 3 injections and 70% received their first 4 (data provided by [name], Alkermes, 2014).

The Lee et al study most closely resembles the one proposed here, however our study has a stronger control group than Lee et al because patients in our control group will be offered XR-NTX at NET Steps after reentry and all participants will have a Patient Benefits Manager to help reinstate benefits that were lost while incarcerated. Putting these data together, we estimate a 23-33% group difference in relapse rates by month 3. Power estimates calculated using this estimate and following the recommendations of Cohen with a 2-sided alpha of .05 and a baseline sample size of 100 per group result in 80% power to detect a difference in relapse rates of approximately 20% (OR = 2.4) between the two groups assuming a relapse rate of 50% in the control condition and 10% and 20% attrition by the 3- and 6-month follow-ups. These outcomes are clinically meaningful based on the severe consequences from untreated opioid addiction, the evidence that continuing in treatment reduces them, and confirmation of their importance by conversations with ex-prisoners and the Recovery Specialists, and focus group participants.

13.4 Secondary Aims:

- 1) Quality of life;
- 2) Weeks in treatment through month six;
- 3) Time to relapse;
- 4) Rearrests;
- 5) Psychiatric symptoms;
- 6) Opioid use;
- 7) Alcohol and other drug use;
- 8) HIV risk;
- 9) Reincarceration;
- 10) Deaths.

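### Section 5.5 allows randomization before a release date is known, so Group A members can leave uninjected and some participants may have no post-release outcome; section 13.3 allows only for attrition

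*Combined protocol and SAP*

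**What the plan says.** **Sequence in 5.5.** "Candidates who complete all inclusion procedures will be randomized into two groups". Group A is then booked to come back before re-entry for a drug test, breathalyzer, pregnancy test where relevant, naloxone challenge and first injection. Group B is booked for the same purpose after release. The length of the gap between randomization and the Group A visit is not stated. The release date enters later in the same section: the benefits manager books an appointment with participants who "have met the inclusion criteria, have been randomized, and have a valid release date".

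**Eligibility (5.2, 5.3).** The custody-related inclusion criterion is that the candidate is not about to be moved to a State or Federal prison for a longer sentence. No criterion asks for a release date.

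**Schedule (7.2).** Randomization, the naloxone challenge and the Day 1 dose all stand in the Week 1 baseline/enrollment block. The dose carries a footnote that it may be given before or after release.

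**Setting (4.3.2).** "Turnover is rapid, and about 50% are released within two weeks". About a third of inmates are sentenced.

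**Analysis (13.2, 13.5).** The primary outcome is relapse during the three months after release. All randomized participants are analysed.

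**Power (13.3).** With 100 randomized to each arm and a two-sided 5% level, the design is said to "result in 80% power to detect a difference in relapse rates of approximately 20% (OR = 2.4) between the two groups". The inputs are 50% relapse among controls, with losses of 10% by month 3 and 20% by month 6. The expected effect is larger: "we estimate a 23-33% group difference in relapse rates by month 3".

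**Timeline (4.2).** "recruitment finished by the end of month 27, and treatment finished by the end of month 33".

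**The concern.** The trial compares a first injection before re-entry with a first injection after it. If allocation is fixed while the release date is still open, two things can happen between randomization and the first dose.

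1. A Group A member is released before the injection visit. That person enters the community untreated, as a Group B member does, but is analysed in Group A. The effect is one-sided, because Group B's first dose follows release anyway, and it shrinks the difference.
2. A member of either arm is not released within the study period. The primary outcome is counted from release, so it does not exist for that person.

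No rule covers a Group A member released uninjected, or a participant held longer than six months. Sections 5.1 and 5.5 provide for holdover only for Group A members already injected, and they disagree: 5.1 provides a further injection before the new release date, while 5.5 rules out a second injection inside the prison. Those two sections must be reconciled; no view is taken here on which is right.

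At stake are power and a complete primary outcome. Both losses would come partly from when the study randomizes, not only from the strategies being compared.

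**Working it through.** **Inputs from section 13.3.** Two-sided alpha 0.05; 100 per arm; 10% attrition by month 3, so 100 × 0.90 = 90 evaluable per arm; control relapse 50%; detectable difference about 20 points (OR 2.4); expected difference 23 to 33 points.

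**Step 1: reproduce the plan's figure.** The section cites Cohen, so use the arcsine effect size:

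h = 2·arcsin√0.50 − 2·arcsin√0.30 = 1.5708 − 1.1593 = 0.4115

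Power = Φ(h·√(n/2) − 1.96) = Φ(0.4115 × √45 − 1.96) = Φ(0.80) = 78.8%

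OR 2.4 against 50% means a relapse rate of 1/(1 + 2.4) = 29.4% and gives 81.2%. The stated 80% is reproduced.

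**Step 2: dilution.** Let f be the fraction of Group A released uninjected. Assume they relapse at the control rate. With a true difference d among the rest, the Group A rate is

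(1 − f)(0.50 − d) + f × 0.50 = 0.50 − d(1 − f),

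so the intent-to-treat difference is d(1 − f). Example: d = 20 points and f = 10% gives 18 points, a Group A rate of 32%, h = 1.5708 − 1.2025 = 0.3683, and power Φ(0.51) = 69.5%.

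Power with 90 per arm (arcsine):

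| True difference | f = 0 | f = 10% | f = 20% |
|---|---|---|---|
| 20 points | 78.8% | 69.5% | 58.9% |
| 23 points | 89.4% | 81.7% | 71.5% |
| 28 points | 97.9% | 94.3% | 87.6% |
| 33 points | 99.8% | 98.9% | 96.2% |

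The pooled-variance formula agrees within 0.3 points in every cell. By that formula, restoring 80% power for a 20-point difference with 10% attrition takes 130 per arm at f = 10% and 166 at f = 20%, against 104 at f = 0.

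**Step 3: non-release.** Let g be the fraction of each arm without a post-release outcome, taken in addition to the 10% attrition. Evaluable n = 90(1 − g). For a 20-point difference (pooled formula):

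| g | n per arm | f = 0 | f = 10% | f = 20% |
|---|---|---|---|---|
| 5% | 85.5 | 76.6% | 67.0% | 56.4% |
| 10% | 81 | 74.3% | 64.6% | 54.2% |

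Section 13.3 does not say what its attrition covers. If it was meant to include non-release, this extra loss is already partly or wholly counted.

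**Step 4: timeline.** Last randomization at month 27 plus six months is month 33, the stated end of treatment. If follow-up counts from release, any wait between randomization and release pushes the last month-6 visit past month 33. The primary time point has slack: 27 + 3 = 30, three months before the end.

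**The case against.** **The gap may be short in practice.** Section 7.2 puts randomization and the Day 1 dose in one block, the study flow table gives a 14-day baseline window, and 5.1 and 5.5 speak of a reported or expected release date. This stands as far as it goes. But no text requires a short gap, and 5.5 describes a separate return visit.

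**The release-date sentence is about something else.** A reader might infer from "have met the inclusion criteria, have been randomized, and have a valid release date" that the protocol places the release date after randomization. It does not say so; the sentence governs when the benefits manager books an appointment. The point rests on the randomization sentence in 5.5 together with the absence of a release-date criterion.

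**The turnover figure is from a wider population.** A reader might infer that half of Group A would leave before injection. The documents do not support that. The figure covers all inmates, and candidates must first be detoxified, respond to a flyer, consent, pass the quiz and complete screening, so many short-stay inmates would have left by then.

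**Some cases are already handled.** Section 5.2 excludes those being transferred to State or Federal prison. Injected Group A members who are held over have their schedule reset under 5.1 and 5.5, so they keep a post-release window. Both provisions narrow the problem, but neither covers release before injection.

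**Missed pre-release doses belong to the real-world strategy.** This is partly right, and it is a reason to keep intent-to-treat. It does not justify adding misses caused by randomizing earlier than necessary.

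**Conclusion.** The concern holds in a limited form. Sections 5.5 and 7.2 leave the order of randomization and release-date confirmation unclear. Under 5.5 as written, participants can be randomized who then miss the assigned pre-release injection or never reach the outcome window. Section 13.3 makes no stated allowance for either beyond attrition.

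The size cannot be derived from the documents. The results rest on assumed fractions of 10% and 20%, and on uninjected Group A members relapsing exactly as Group B does. On those assumptions the loss is about 9 or 20 points of power at the 20-point difference on which the stated 80% rests, and about 8 or 18 points at a 23-point difference.

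A reader might infer that the trial is underpowered. That does not follow: with 10% uninjected, power stays above 80% across the plan's expected 23 to 33 points, and at 28 points or more it stays at 87.6% or above even with 20% uninjected. Missing post-release outcomes remain a problem at any effect size.

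Nor does the timeline lack slack altogether. Only the month-6 follow-up is tight, and section 4.2 calls its recruitment dates a best estimate. This is a cheap improvement to the plan, not a demonstrated failure of it.

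**What to change.** - Make 5.5 agree with 7.2. Leave consent, quiz and screening as they are. In both arms, randomize as the last step after screening, once a release date is on record and immediately before the first-dose visit is scheduled.
- Record candidates who leave before that step as screen failures, using the log the protocol already requires.
- Keep the intent-to-treat analysis. Report by arm the numbers released uninjected (Group A) and the numbers not released in time for the primary outcome.
- Check that month-6 follow-up counted from release fits the month-33 end, and set the last randomization date accordingly.
- Reconcile the holdover rules in 5.1 and 5.5.

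A fixed cut-off, such as a release date within 14 days, is not needed. It could narrow the unsentenced stratum that the trial deliberately includes, and it would shorten the time for benefits work before re-entry. Waiting for a release date need not cost that work much, since under 5.5 the benefits appointment already depends on one.

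The cost is protocol wording and the order of one step. Expect somewhat more screen failures and some under-representation of inmates whose release is unpredictable. Release dates will still slip after randomization, so the change reduces both losses without removing them; that is why the by-arm reporting is needed.

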4. STUDY DESIGN/TIMELINE/ AND RESEARCH SITES

4.1 Study Design:

To address these questions we will identify opioid addicted prisoners who appear to meet study admission criteria and express interest in XR-NTX treatment, explain the study to them in detail, encourage them to ask questions, and obtain consent from those who remain interested. We will then complete baseline assessments to confirm eligibility (criteria described later) and the first 200 that meet enrollment criteria will be stratified according to male/female and sentenced/not sentenced (e.g. meet/not meet with probation/parole officer), and randomized 1:1 to receive XR-NTX before reentry with the offer of having three additional doses of XR-NTX at NET Steps after reentry, or be given an appointment to be seen at NET Steps same day or up to 7 calendar days after release to receive their first dose of XR-NTX after reentry with the opportunity for 3 additional doses at NET Steps. Follow-ups for participants who have difficulty going to the NETSteps site can have their follow-up injections and assessments done at the [name]. All participants will be assigned a Patient Benefits Manager to help reinstate benefits that were lost during incarceration and all will receive the usual counseling and other services available to NET Steps patients (described later in more detail). A urine drug toxicology screen , adverse events, and an alcohol breathalyzer test will be done weekly and brief assessments will be done at months 1, 2, 4 and 5 with more detailed assessments at months 3 and 6. Criminal justice information on arrests and re-incarcerations will supplement the assessments.

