5 ENROLLMENT AND WITHDRAWAL

5.1 Enrollment

Two hundred (200) prisoners meeting enrollment criteria will be enrolled and stratified according to male/female and sentenced/non-sentenced (e.g. required vs. not required to meet with a probation officer), and randomized to receive XR-NTX before re-entry with follow-up XR-NTX treatment at NET Steps, or randomized to receive their first dose of XR-NTX when they report to NET Steps same day of release up to 30 calendar days post release. Should a prisoner not be released from PPS at the reported release date, and has received his baseline injection of Vivitrol, and the extended incarceration exceeds 30 days, the study will reset his baseline date and administer a 2nd pre-release restart shot prior to the new release date. Additional reset injections may be needed if new release dates are not met. Prisoners will be told that three additional XR-NTX doses will be available at NET Steps and that if they change their mind after reentry they can receive another treatment of their choice. Urine drug tests, adverse events, and a breathalyzer will be done weekly with brief assessments at months 1, 2, 4 and 5, and more detailed assessments at months 3 and 6. PPS data and publicly available criminal justice system information (<http://ujportal.pacourts.us/docketsheets/cp.aspx>) will document rearrests and re-incarcerations. Reasons for screen failure will be recorded; those who relapse will be restarted on XR-NTX or offered the most appropriate treatment at NET Steps or another program of their choice. Efforts will be made to obtain follow-up data on all participants according to the intent to treat design.

5.2 Inclusion criteria:

Opioid dependent with physiological features according to DSM-5; interested in XR-NTX treatment; eligible to have health benefits reinstated; detoxified; age 18 or above; not being transferred to serve a longer sentence in a State or Federal prison; provide their address or phone number along with the names and contact information of

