7. STUDY SCHEDULE OF EVENTS

ASSESSMENT SCHEDULE 7.1 Screening:
	
 - Quiz completed, scored, and reviewed - Informed consent completed and signed - Check of inclusion and exclusion criteria - DSM-5 Checklist - medical/surgical history, including neurological and psychiatric history - physical exam, including a neurological assessment - Vitals- heart rate and blood pressure - height and weight - hematology-Hb,Ht,WBC-diff, platelets* - biochemistry (ALT, AST, ALP, creatinine)* - HCV test, HBV* - HIV test - urine or blood pregnancy test (for women of childbearing potential)
---	--

	
 - Prior/concomitant meds • Drawn by Study if not using historical data - ASI (baseline) - EuroQol - BDI - TLFB - RAB - smoking status

7.2 Baseline/ Enrollment (Week 1)
	
 - Randomization - urine drug tox screen - breathalyzer - urine or blood pregnancy test (for women of childbearing potential) - naloxone challenge* - XR-NTX administered (Day 1)* - recording of AEs/SAEs, if any- Locator Data - Non medical services form - pt satisfaction questionnaire - Check counselling enrollment 
* pre-release or post release

7.3 Week 2 through end of Month 5
	
 - naloxone challenge (at monthly injections/can be clinical observation) - XR-NTX adminis. (mo 2, mo 3, mo 4) - ASI (month 3) - EuroQol (month 3) - BDI (month 3) - urine or blood pregnancy test (monthly) - TLFB (mo 1, mo 2, mo 3, mo 4, mo 5) - RAB (Month 3) - urine drug tox screen (weekly) - alcohol breathalyzer test (weekly) - Non medical services form - record all primary and secondary efficacy in CRF - recording of AEs/SAEs, if any- recording of concomitant medications - check for protocol violations - check time to restoration of benefits - check deaths report -check re-incarceration report - Locator Data

	
 - Check counselling enrollment - End-of-study CRF (if needed) - Pt Remuneration made

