12) Quality of Life: measured by the EuroQol (EuroQol Group, 1990), a standardized measure for describing and valuing health-related quality of life. It consists of two components: one that describes current health in five domains, by choosing one of three levels in each of five domains: mobility, self-care, usual activities, pain/discomfort, and anxiety/depression; and the other a visual analogue scale where patients rate their current global health state by choosing a number from a visual analogue scale that ranges from 0 to 100- where 0 represents the worst imaginable health and 100 is the best imaginable health. It was used in the cost-effectiveness study of short vs. longer-term buprenorphine-naloxone treatment for opioid addicted youth where it showed improvement with addiction treatment (Polsky et al, 2010), and will be done at baseline using the timeframe “when you entered the PPS”, and at 12 and 24 weeks using the timeframe “since your last assessment”.

13) Psychiatric Symptoms: measured by the Psychiatric Composite Score of the ASI and the Beck Depression Inventory (BDI; Beck et al, 1961) for 30 days prior to incarceration at baseline and at 12 and 24 weeks after reentry.

14) HIV Drug and Sex Risk: Done at baseline and at 12 and 24 weeks using the Risk Assessment Battery (RAB), a self-report of drug use and injection and sex risk behaviors (Navaline et al, 1994; [name] et al, 2001) that will assess HIV risk over the 12 weeks prior to incarceration at baseline and the past 12 weeks at each follow-up. The RAB has 38 closed end items that cover issues of substance use including frequency, needle sharing and cleaning, and condom use. Responses on the RAB have been equivalent to those collected by

personal interview, and scores were able to discriminate between cocaine and opioid abusers as well as those who converted to HIV+ from those who remained HIV negative ([name] et al, 2001).

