13 STATISTICAL HYPOTHESES AND PLAN

13.1 Primary Aims

Before performing analyses, we will apply the following data screening and cleaning procedures: 1) screen for data-entry errors; 2) check for outliers; 3) assess the extent and pattern of missing data, and 4) check that appropriate assumptions of normality are met, as necessary. In all analyses, we will examine whether the assumptions underlying the application of statistical methods have been met, principally through use of standardized residuals, influence diagnostics, and graphical displays. We will check to confirm that the groups do not differ on baseline relevant background variables using analyses of variance (ANOVA) for continuous variables and log-linear models for binary or ordinal responses. The randomization process should minimize the need for inclusion of covariates to reduce bias in treatment comparisons. However, we will consider relevant covariates for inclusion in analyses to improve precision of estimation of treatment effects (Hauck et al. 1998). The statistical procedures that will be used to examine each outcome are listed below.

13.2 Primary Aim 1—Proportion Without Relapse by Month 3:

At each monthly assessment we will determine whether a subject has relapsed based on self-report, physical examination, response to a naloxone challenge, or information from program staff of significant others. Using these data, we will create a binary outcome reflecting whether or not the participant relapsed during the 3 months post-release. We will compare the proportion of participants who relapsed in the two groups using a logistic regression analysis. The analysis will include group as a predictor variable along with all relevant covariates (including the stratification variables). Relapsed will be defined by self-report of 10 or more days in the past 30 days or by two or more opiate positive urine samples in the last 30 days. Positive urine samples will be computed as 5 days of opioid use for each sample. The analysis will be performed using SAS's PROC LOGISTIC.

13.3 Power Analyses for Primary Aim:

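### Visits appear to be counted from the first injection but the primary outcome from release, and no rule links the two; if the month-3 visit closes the window, Group A is read after fewer days at liberty

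*Combined protocol and SAP*

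**What the plan says.** All places are in the combined protocol and SAP.

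- **Section 7.2** (Baseline/Enrollment, Week 1) lists "XR-NTX administered (Day 1" with an asterisk explained as "pre-release or post release".
- **Section 5.5**, Group A held no more than 30 days from the first injection: "the subject’s next injection will be considered his 2nd injection and his visit schedule will not change".
- **Section 5.5**, Group A held longer: "The injection visit dates will be reset to begin as his first injection, with the next injection post release". Section 5.1 also resets, but describes the injections differently: "the study will reset his baseline date and administer a 2nd pre-release restart shot prior to the new release date".
- **Section 4.1**, Group B is to "be given an appointment to be seen at NET Steps same day or up to 7 calendar days after release". Section 5.5 also gives 7 days; section 5.1 allows up to 30 calendar days.
- **Section 3.1.1** gives the primary outcome as the proportion not relapsed by month three, with no time zero.
- **Section 13.2** makes it a binary variable for "whether or not the participant relapsed during the 3 months post-release", with relapse determined at each monthly assessment using a 30-day look-back.
- **Section 8.1**, item 13, takes psychiatric symptoms "for 30 days prior to incarceration at baseline and at 12 and 24 weeks after reentry". Item 19 times the employment score in the same way.
- **Section 5.6** spaces follow-up assessments every 4 weeks to month 6. Sections 4.1 and 7.3 continue weekly urines and monthly TLFB past month 3.

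**The concern.** Two clocks are in use. The visits appear to be counted from the injection, and the primary outcome and several secondary measures are counted from release. Release comes after Day 1 in Group A and on or before Day 1 in Group B, so a visit with the same number falls at different times since release in the two arms. The protocol resets the calendar for long holds but not for holds of up to 30 days, nor for the ordinary interval between a pre-release injection and release.

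An analyst who takes the month-3 visit as the end of the primary window would count Group A's relapses over a shorter time at liberty than Group B's. That lowers Group A's relapse proportion even if timing of the first dose makes no difference, and it does so in the direction of the hypothesis. The trial is open-label (section 16.2), so a window left undefined could be settled after results by arm have been seen. The month-3 and month-6 quality-of-life, psychiatric and HIV-risk measures would also be taken at different times since reentry by arm.

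**Working it through.** **Planned power.** Inputs from section 13.3: 100 per group, 10% attrition by month 3 (so 90 per group), 50% control relapse, a difference of about 20 points or OR 2.4, two-sided alpha 0.05, power 80%. A two-proportion normal test with pooled variance gives 78.7% for 50% vs 30%. OR 2.4 means odds of 1/2.4, or 29.4%, and gives 81.1%. The stated 80% is reproduced.

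**Days at liberty at the month-3 visit.** With 4-week spacing, month 3 is day T = 84 from the first injection. Let *a* be the days from injection to release in Group A and *b* the days from release to injection in Group B.

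- Group A: 84 − *a*. With *a* from 0 to 30, this is 54 to 84.
- Group B: 84 + *b*. With *b* from 0 to 7, this is 84 to 91; with *b* up to 30 (section 5.1), it reaches 114.
- Largest gap: 91 − 54 = 37 days, or 114 − 54 = 60 days.

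**Effect with no drug effect, if the month-3 visit closes the window.** Both arms have the same relapse-time distribution from release, set to the plan's 50% at day 84: p(d) = 1 − exp[−ln 2 × (d/84)^k]. Constant hazard is k = 1. Section 13.3 says relapse typically comes in the first days or weeks, so k = 0.5 is also shown; that value is an assumption. For k = 1: p(54) = 36.0%, p(77) = 47.0%, p(91) = 52.8%. When a share f of Group A is held 30 days and the rest have *a* = 0, Group A's rate is (1 − f) × 50% + f × p(54). The values of *a*, *b* and f below are assumptions. The last two columns give the chance of a significant result in a two-sided 0.05 unadjusted test with 90 per group.

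| Scenario | A vs B, k = 1 | A vs B, k = 0.5 | Error, k = 1 | Error, k = 0.5 |
|---|---|---|---|---|
| 10% of A held 30 days; B seen on release day | 48.6% vs 50.0% | 49.3% vs 50.0% | 5.4% | 5.1% |
| All A injected 7 days before release; all B seen on day 7 | 47.0% vs 52.8% | 48.5% vs 51.4% | 12.1% | 6.7% |
| 25% of A held 30 days; all B seen on day 7 | 46.5% vs 52.8% | 48.2% vs 51.4% | 13.5% | 7.2% |
| Extreme: all A held 30 days; all B seen on day 7 | 36.0% vs 52.8% | 42.6% vs 51.4% | 62.5% | 21.7% |

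The differences are about 1 point in the first row, 3 to 6 in the middle two, and 9 to 17 in the extreme. Taking month 3 as day 90 gives slightly smaller figures (12.1% becomes 11.1%; 62.5% becomes 55.9%).

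**If the window is cut at three months from release.** Both arms have the same time at risk, so the difference is 0 and the error rate 5%. For a Group A participant held 30 days, the month-3, month-4 and month-5 visits fall on days 84 − 30 = 54, 112 − 30 = 82 and 140 − 30 = 110 after release. Data to day 90 are therefore scheduled, but at visits numbered 4 and 5, and the plan does not say to use them for a month-3 outcome. The month-1 visit (day 28) would fall in custody.

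**The case against.** The strongest reply is that section 13.2 already fixes the window at three months after release in both arms. No section says that the month-3 visit closes it, and urine and TLFB data continue to month 6. Read strictly, the bias disappears. This stands, and it is why the bias is conditional. It does not dispose of the point, because the same section builds the outcome from the monthly assessments and gives no rule for moving from visit number to days since release.

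The anchor is also partly inferred. The Week 1 row that contains Day 1 also contains randomization, which section 5.5 places before Group B's post-release visit. The sentence in 5.5 about an unchanged schedule could refer to injection visits only, and the reentry wording in 8.1 suggests that assessments were meant to run from release. That is fair. It shows that the sections need reconciling, not that they agree.

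The size is uncertain. The documents do not give the pre-release interval, the share held or the length of holds, and early relapse shrinks the effect. A Group B participant seen on the day of release has no shift at all.

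A reader might infer that the primary result is bound to favour Group A. The documents do not support that. It requires the month-3 visit to close the window, and the direction is derived only for no drug effect. With an active drug, a hold also uses up part of the first injection's cover in jail, which works against Group A.

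**Conclusion.** The defect is an unresolved conflict between visits that appear to run from the injection and a primary window that runs from release. It affects the primary endpoint and should be settled before analysis. If the month-3 visit closes the window, relapse is understated in Group A relative to Group B under no drug effect: about 1 point in a mild scenario, 3 to 6 points in moderate ones, and 9 to 17 points only if all of Group A were held 30 days and all of Group B came on day 7. The design difference is about 20 points. These figures rest on the plan's 50% relapse rate, an assumed hazard shape and assumed intervals, and on Group B's calendar running from its own injection. With the window cut at three months from release, the bias is zero and planned power is unaffected.

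**What to change.** - **Primary outcome (13.2).** Name the release date, available from Lock & Track, as time zero in both arms. Classify relapse from dated urine and TLFB data in days 0 to 90 after release, whatever the visit number, using month-4 and month-5 data where needed. Report days at liberty by arm.
- **Early days in Group B.** State how use between release and the first visit is captured. Under the 30-day rule the month-1 visit can fall on day 30 + 28 = 58, and its 30-day look-back reaches only to day 28.
- **Month-3 and month-6 secondary measures.** Record days since release and use it as the time variable, or schedule these assessments from release.
- **Text.** Reconcile 4.1, 5.1, 5.5 and 7.2 with each other and with 8.1 and 13.2, including the 7-day and 30-day limits for Group B and the differing accounts of long holds. Injection timing is left to the sponsor.

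The cost is a few sentences in the plan and slightly more data handling. The primary outcome needs no separate site calendar. If assessments are rescheduled from release, some will no longer coincide with injection visits, which is a burden where follow-up is already a named risk (5.9).
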